Minimizing Risk: Certain studies at our institution draw over 7ml/kg in 6 weeks, or up to 7 ml/kg in a single draw, but include iron supplementation. Otherwise, the routine guidelines in our Pediatric CTSC are 2.5ml/kg for a single draw and no more than 5 ml/kg over a 4 week period. Our baseline visit will include 11.5 ml of blood (HbA1c, Hb, Cr, AST, ALT) and 25.5 ml of blood for PCOS patients (additional draw for T4, TSH, prolactin, LH, FSH, 17OH progesterone and DHEAS). The OGTT visit includes up to 300 ml of blood which will occur within 4 weeks of the initial visit. Thus, our OGTT visit is within the NIH Clinical Center guidelines of 9 ml/kg in 6-8 weeks and within Children's Hospital Colorado's institutional guidelines of 5 ml/kg. In addition, by study design, subjects are screened by our baseline CBC and excluded if anemic, further increasing the safety of the study regarding blood draws. We will use a minimum weight cutoff of 38 kg to remain below the most conservative pediatric CTSC blood drawing guidelines. This screening also helps to increase the safety of the blood draw. In addition, the blood planned to be frozen and held could also be

omitted if needed to reduce blood volume for a particular subject. Finally, our CTRC has a system to track other studies subjects might enroll in, and we ask during our consent process if the subject has been involved in any other studies in the past 6 weeks to avoid excessive blood drawing.

Justification: Screening laboratory measurements are necessary to assure that patients meet inclusion/exclusion criteria before any further study is completed. A CBC is necessary as a screening lab, to rule out anemia. A hemoglobin A1c can be used to rule out diabetes. Hormone levels of free and total testosterone, and sex hormone binding globulin are needed to categorize patients as having PCOS, and prolactin, DHEAS, LH, FSH, TSH, total T4 or 17-OH progesterone to rule out other causes of oligomenorrhea, if not done previously.

2. IV Risks

Description: One peripheral IV will be placed during the OGTT for drawing blood samples.

Risk: There is temporary discomfort when the needle goes in and 10% of the time there is a small amount of bleeding under the skin that may produce a bruise. Rarely, there is a risk of a blood clot forming or infection. We will use a low dose of a medication called heparin to try to prevent blood clotting.

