Justification/Minimization: These studies involve sampling blood at multiple time points. Thus, an IV is needed, so as to avoid multiple needle sticks. These studies are focused on measured rates of change which necessitates the sampling of the same test over time. Proper sterile technique will be used with blood draws and IV placement to decrease the infection risk. EMLA cream will be used if subject desires to minimize pain of IV.

3. Oral Glucose Tolerance Test (OGTT):

Description: An OGTT will be performed with multiple blood draws over 6.5 hours. The purpose of the OGTT is to provide a controlled oral stimulus to effect changes in lipolysis and hepatic glucose release. Subjects will also drink a glucose+fructose drink as part of the liver spectroscopy.

Risk: The subjects rarely experience nausea within 15 min of consuming the drink, however, the amount of carbohydrate is very similar to a large soda, which is regularly consumed by this patient population.

Justification/Minimization: A standard oral challenge is needed to study lipogenesis, lipolysis and gluconeogenesis in the fed state. We have chosen to start with a standard glucose and fructose load, to simplify the mathematical modeling. Dynamic carbohydrate metabolism in youth is made more relevant by the recently reported TODAY study, showing a decline in beta cell function in youth with newly diagnosed type 2 diabetes that was much more rapid than what has been reported in adults, and not prevented by metformin in the majority of the youth⁴⁹. Our team of investigators, CTRC pediatric research nursing staff and physicians are well experienced with the OGTT blood draw procedure. A floor nurse located on the 9th floor of CHC will be available during our inpatient visits and patients will be distracted by TV or other similar means during the OGTT, to minimize queasiness.

4. Stable Isotope Studies:

Description: Oral stable isotope tracer of glycerol will be utilized to determine rates of intrahepatic substrate flux. These are substances normally present or produced in the body, and thus pose no more risk than typical glucose infusions. Measurements of these metabolic processes are only able to be made with the utilization of stable isotope tracers.

Risk: We are utilizing an isotope which already exists in all humans, but are simply increasing the percentage. We are only giving this medication orally. These are NOT radioactive substances.

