Justification/Minimization: Sterile and pyrogen-free ²C13 glycerol will be obtained from the manufacturer and delivered to CHCO IDS. The IDS pharmacist will deliver the tracer to the 9th floor inpatient CTRC once ordered by the physician.

5: Finger stick for glucose measurement during MRI:

Description: A glucometer will be utilized to measure fasting and 1 hour blood sugars following the glucose drink in the MRI. (Pending scheduling)

Risk: There is a small amount of pain with the finger poke and risk of infection.

Justification/Minimization: The change in blood sugar needs to be assessed to correlate with changes in the glucose-6-phosphate concentrations. The finger will be well cleaned and dried with an alcohol pad. One-time use Lancet's will be utilized to avoid the potential for blood exposure to other patients that has occurred with multi-use Lancet devices.

6. Standard Diet

Description: A dinner and snack will be provided from the CTRC the night prior to the OGTT. The diet will be composed of 65% carbohydrates, 25% fat, and 10% protein at 1.25 daily needs and will be will be provided by the CTRC.

Risk: None

Justification/Minimization: 1.25 x weight maintenance was chosen as this as most similar to our subjects food consumption based on pilot subject's food frequency questionnaires and optimal for detection of hepatic Ra ⁴⁶.

7. Magnetic Resonance Imaging (MRI)

Description: The MRI will usually be obtained the day of admission to CHC), at the UCD Brain Imaging Center on the Fitzsimmons campus. A trained research radiographer who is supervised by [name], of UCD radiology, will perform an abdominal MRI to obtain hepatic, visceral and subcutaneous fat on a 3.0 T whole-body MRI scanner (Siemens MAGNETOM, Malverne, PA). Subjects will lie supine while these measurements are obtained, need to hold reasonably still during the scan and cannot weigh >325 lbs. A second sequence to measure the amount of fibrosis (if any present) in the liver will be performed. In some subjects, a specialized phosphorus coil will be utilized to measure the concentration of ³¹P via MRS to calculate glucose-6-Phosphate concentrations before and after the glucose drink.

Risks: Minimal. Subjects may develop claustrophobia in the magnet.

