Description: The metabolic cart measures the amount of air that the subject breathes in and out. The machine attaches to the subject's mouth through a tube, or a plastic bubble that is placed over the subject's head. There is the potential for experiencing claustrophobia from having the plastic bubble over the subject's head. A metabolic cart will be utilized multiple times during the OGTT study day to measure rates of oxygen consumption and carbon dioxide release. These rates can be utilized to calculate rates of carbohydrate and fat oxidation and resting energy expenditure.

Risk: Minimal risk of claustrophobia.

Justification/Minimization: These studies are well tolerated by youth, and involve placing a clear plastic hood over the subjects head for approximately 20 minutes. The data collected from the baseline study is also very useful for assisting obese subjects in determining their true caloric needs, and useful in setting dietary goals for weight loss. This piece of information is thus utilized in post-study nutritional counseling.

13. Food Frequency Questionnaire (SEARCH FFQ)

Description: Customary macronutrient pattern will be ascertained by diet interview at the time of admission using a SEARCH FFQ, modified to incorporate common food choices among ethnically and regionally diverse youth aged 10-19 participating in another large childhood diabetes study, SEARCH (48). The instrument is self-administered with staff support to provide instructions, answer questions, and to review the form after completion, and captures the last week of dietary intake.

Risk: None

Justification/Minimization: Several of the measurements being assed are affected by prior nutritional intake. Furthermore, subjects will receive dietary counseling at the end of the study, and by knowing

what their previous dietary pattern is, suggestions for improvement can be tailored to their specific dietary habits.

14. 3DPar Questionnaire

Description: A questionnaire (3DPAR) recalling the physical activity levels of the three previous days will be completed at visit 3. screening.

Risk: None

Justification/Minimization: Physical activity can directly affect insulin sensitivity, our primary outcome measure. The 3DPar is a well validated measure to asses 3 days of physical activity in youth, and includes a variety of youth centric activities.

15. Strengths and Difficulties Questionnaire:

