No protected health information will be collected until the appropriate HIPAA forms are completed. The protected health information that will be collected will include: Name and phone number, demographic information (DOB, sex, ethnicity, address, etc.), diagnosis (es), history and physical, laboratory or tissue studies, radiology studies, procedure results, survey/questionnaire results, research visit records, and portions of previous Medical Records that are relevant to this study. This information will be accessible only by the study investigators, Federal agencies overseeing human subject research, the Colorado Multiple Institutional Review Board, regulatory officials from the institution where the research is being conducted to monitor safety and compliance with policies.

A. Adverse Events (AE)

The OGTT is a standard procedure used in a large number of research studies and settings. Adverse events are uncommon when the procedure is done by experienced personnel in an appropriate setting.

1. Adverse Event Definition

For the purposes of this study, an Adverse Event (AE) is defined as any significantly abnormal physical finding identified on examination and any significantly abnormal laboratory result obtained on the patient between visits or at the time of the visit. Questions answered YES and any new abnormal physical findings are pursued by the study staff in order to determine the seriousness of the event and the need for further evaluation, follow-up, or referral. If follow-up or referral of abnormal research results or procedure is required, the PI will place a referral in EPIC, update the PCP on patient condition and reason for referral and contact family to discuss follow-up treatment options.

a) Adverse Event Reporting

AEs are reported on a standard form that is completed by the study staff at each regular follow-up visit and phone interview. Adverse events reported or ascertained between clinic visits are captured and reported at the time of the next scheduled visit.

Pre-existing conditions (that is, conditions present prior to study enrollment) are not considered or recorded as AEs or SAEs unless the condition worsens in intensity or frequency after enrollment. Likewise, continuing adverse events are not reported as AEs at subsequent visits unless they increase in severity or frequency between the visits, they result in criteria for an SAE, and/or they resolve between visits.

B. Serious Adverse Events (SAE)

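### The adverse-event definition is limited to examination findings and laboratory results, so the symptom-only harms that the protocol lists do not meet it and their recording is not assured

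*Combined protocol and SAP*

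**What the plan says.** Section VI.A.1 (Adverse Event Definition) sets the rule: "an Adverse Event (AE) is defined as any significantly abnormal physical finding identified on examination and any significantly abnormal laboratory result", whether obtained at a visit or between visits. It continues: "Questions answered YES and any new abnormal physical findings are pursued by the study staff in order to determine the seriousness of the event", together with the need for further evaluation, follow-up or referral.

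Section VI.A.1.a (Adverse Event Reporting) says when events are logged: "AEs are reported on a standard form that is completed by the study staff at each regular follow-up visit and phone interview". It adds: "Adverse events reported or ascertained between clinic visits are captured and reported at the time of the next scheduled visit".

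The risks that the protocol expects are in Section III.D. For the OGTT (item 3): "The subjects rarely experience nausea within 15 min of consuming the drink". For the MRI (item 7): "Subjects may develop claustrophobia in the magnet". For the metabolic cart (item 12): "Minimal risk of claustrophobia". The finger stick (item 5) carries a little pain and a risk of infection. For the IV line (item 2), about 10% of placements cause "a small amount of bleeding under the skin that may produce a bruise".

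Section VI.B.1 makes an adverse event serious when it meets one of a list of criteria. Section VI.D triggers a consultation before further study visits if one or more participants have a listed serious event.

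**The concern.** An adverse-event definition decides what goes on the form. If it admits only signs and laboratory values, a participant can have exactly the reaction that the protocol predicted without any event being recordable. The investigator reports adverse events to the institutional review board and the research centre, and writes a yearly report for both (Section VI). That report can be no more complete than the definition behind it. The study enrols girls from age 12, and the participant burden comes mainly from procedures whose listed risks include discomfort and distress. What is at stake is whether a reader of the safety record can tell how well these procedures were tolerated.

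**Working it through.** No arithmetic applies. The documents give no adverse-event count or threshold, and the only word on the frequency of nausea is that it is rare. The check sets the definition beside the listed risks, the recording rules and the study calendar.

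**1. Scope.** The defining sentence has two limbs, an examination finding and a laboratory result, and each must be significantly abnormal. There is no limb for a complaint or symptom.

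**2. Listed harms against that scope.**
- IV-site bruising (III.D.2) and infection at a puncture site (III.D.2 and III.D.5) can be seen on examination. They are covered if judged significantly abnormal.
- Nausea after the drink (III.D.3) is a symptom, so it is not covered.
- Finger-stick pain (III.D.5) is a symptom, so it is not covered.
- Claustrophobia in the scanner (III.D.7) and under the hood (III.D.12) is a symptom, so it is not covered.

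The 10% bruising figure is the only numerical frequency among these, and it belongs to a harm that the definition can already take in.

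**3. The sentence on yes answers.** It places yes answers beside new physical findings and calls the result an event, which suggests that symptom questions are asked. It stops at judging seriousness and the need for referral, and does not say that a yes is entered on the form. The questions are not identified. The closest text is the Visit 3 admission questioning on changes in medication and medical history (Section III.C). That comes before the next morning's OGTT and is not linked to the adverse-event form.

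**4. Timing.** The study calendar (Section III.C) has no row for adverse-event enquiry and places the history and physical at Visit 1 only. The MRI and finger stick are at Visit 2. The OGTT, tracer and metabolic cart are at Visit 3, the last of three visits. An event arising at Visit 3 therefore has no next scheduled visit at which to be captured. The one described later contact is a call within 6 months of completion, and its stated purpose is follow-up care and questions about results (Section III.C, Lifestyle Prescription).

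**5. Carry-over.** Under Section VI.B.1 a serious event is an adverse event that meets a further criterion, so an occurrence outside the adverse-event definition is, read literally, outside the serious one too. The stopping criteria in Section VI.D rest on the serious events.

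**6. Other traces.** Intolerance that prevents completion would appear as a withdrawal for inability to complete procedures (Section VI.C). Discomfort that does not stop a procedure leaves no specified record. Section VII has no safety tabulation.

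**The case against.** The best defence is that Section VI.A.1 should be read as a whole. Yes answers stand next to physical findings as candidate events. The reporting text speaks of events reported or ascertained and of intensity, severity and frequency, language that also fits complaints. The standard form is not reproduced, so it may carry symptom items. Visit 3 is an inpatient stay with a nurse available, and staff may treat it as a regular visit for logging. The listed symptoms are minor, safety is not a study outcome, and treatment groups are formed by medication already in use, so no drug-safety comparison is lost.

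Much of this stands. It rules out one tempting inference, that symptoms will certainly go uncounted and the safety report will show none whatever happens. The documents leave recording undetermined; they do not exclude it. It is also fair that an event grave enough to be serious would usually produce an examination finding, so the practical risk of missing one is small.

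The defence does not remove the defect. The defining sentence is a stated rule, and it excludes symptoms. The sentence that might rescue them gives follow-up without recording, and the timing rules do not clearly reach the visit where most of the procedures occur.

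**Conclusion.** The point holds as a conflict within Section VI.A, with a gap in when events are logged. By its terms the definition leaves out nausea, claustrophobia and procedural pain, all of which the protocol lists, and nothing else in the text assures that they are recorded. The same scope passes into the serious-event definition and the stopping criteria. It affects the 80 participants planned for the MRI and overnight visits. Their number of symptom events cannot be estimated from the documents. The conclusion rests on a literal reading of the definition and on the form being no broader than the text.

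A reader might go further and infer that a participant who vomits or faints would enter the primary analysis as though fully dosed, biasing the flux results. The documents do not support that. They name neither vomiting nor fainting and state no gastrointestinal risk for the tracer. The nausea they describe comes within 15 minutes of a drink taken about 3 hours before the tracer. The primary outcome is expressed as activity ratios (Section III.A) or pathway percentages (Section VII), and no effect of partial dose loss on these is shown. How to analyse an incompletely retained drink or tracer is a separate question that does not follow from the adverse-event wording. The consequence shown here is confined to safety reporting. It is worth correcting because the remedy is specific and cheap.

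**What to change.** Amend Section VI.A and the study calendar as follows:

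- Define an adverse event as any untoward symptom reported by the participant, physical sign or laboratory change, from the first study procedure onward.
- State that a yes answer to a symptom question is entered on the adverse-event form, and list the questions. They should at least cover the harms in Section III.D: nausea, claustrophobia and pain.
- Ask the questions at Visits 2 and 3 before discharge, and add a matching row to the calendar, so that Visit 3 events do not depend on a later visit that is not planned.
- State in Section VI.B.1 that the serious-event definition uses the same scope, so that Section VI.D follows from it.

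The cost is protocol wording, a calendar row and a short set of questions on the form. The downside is a few more minor events to log. The sample size, the procedures and the primary analysis do not change.

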DEXA Scan (located in Leprino building)			X
Oral Glycerol Tracer			X
WatchPAT sleep study			X
EndoPat and Dynapulse		X	
MRI of abdomen and liver,		X	
P MRS of Liver (pending scheduling)		X	
Metabolic Cart			X
Total Time of visit (approximately)	2 Hours	2 Hours	24 Hours
Location of Visit	CHCO CTRC Outpatient	UCD Outpatient Brain Imaging Center	CHCO Inpatient Hospital

The study consists of 3 visits - 2 outpatient visits and one overnight inpatient visit. Inpatient visit will last approximately 24 hours, outpatient screening visit approximately 2 hours, outpatient MRI visit approximately 2 hours. The 3 visits would be completed within 4 months' time.

Overall enrollment procedure plan per group

Test Group	Screening	MRI/MRS	Overnight stay	Oral Glycerol tracer	DEXA
Untreated PCOS	25	20	20	20	20
PCOS w/ Metformin	25	20	20	20	20
PCOS w/ OCP's	25	20	20	20	20
Obese Control	25	20	20	20	20
Total	100	80	80	80	80

VISIT 1 (SCREEN VISIT)

Pediatric CTRC Outpatient unit: Participants will begin with a medical screening and physical exam for inclusion/exclusion criteria evaluation. During this visit, patients will review and complete consent documents, have demographics and medical history confirmed, assess allergies and further evaluation of inclusion/exclusion criteria, have blood samples drawn, and have anthropometrics completed. HbA1c, ALT, AST, CBC panel and testosterone panel will be drawn at the beginning of the visit after consent in all subjects. PCOS subjects will have more labs performed for confirmation of PCOS status, if not performed previously.

Screening lab test	Purpose for test
HbA1C	Rule out type 2 diabetes, if > 6.4% subject to be excluded
ALT, AST	Ensure no severe liver disease, if >150 IU subject to be excluded normal subject is excluded
Hemoglobin & Hematocrit (part of CBC)	If subject is Anemic, they will be excluded
Testosterone	Test for hyperandrogenism – required to meet NIH criteria for PCOS
Optional PCOS labs	
PCOS status must be confirmed prior to enrollment in PCOS group. Referring physicians often do not perform the entire recommend work-up for oligomenorrhea (per 2013 Endocrine Society Clinical Guidelines for PCOS). The values are typically expected in PCOS publications	
TSH, total T4	Ensure no hypo or hyperthyroidism causing amenorrhea
LH, FSH	Rule out primary ovarian failure
17-hydroxyprogesterone	Rule out late onset congenital adrenal hyperplasia
DHEAS	Rule out adrenal tumor
Prolactin	Rule out prolactin secreting brain tumor

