Note: N=Number of participants in the study sample. PPV=Positive predictive value. NPV=Negative predictive value. AUC=Area under the curve analysis. CES-D=Center for Epidemiologic Studies Depression Scale. CES-DC=Center for Epidemiologic Studies Depression Scale Child Version. α =Cronbach's alpha reliability coefficient. K-SADS-PL: The Schedule for Affective Disorders and Schizophrenia for School-Age Children – Present and Lifetime version. MINI-KID: The Mini-International Neuropsychiatric Interview. MINI: The Mini-International Neuropsychiatric Interview for children. K-SADS: The Schedule for Affective Disorders and Schizophrenia for School-Age Children. K-SADS-E: The Schedule for Affective Disorders and Schizophrenia for School-Age Children – Epidemiological version. DISC: The National Institute of Mental Health Diagnostic Interview Schedule for Children. K-SADS-P: The Schedule for Affective Disorders and Schizophrenia for School-Age Children Present Episode version.

LIFESTYLE PRESCRIPTION

The final visit will conclude with education regarding the importance of physical activity, diet and lifestyle modification to mediate the risks associated with sedentary lifestyle and an exercise prescription designed to increase physical activity. The exercise information and prescription are the standard of care used in our Children's Hospital Colorado Pediatric Metabolic Syndrome Clinic, designed by the Children's Hospital Colorado Pediatric Exercise Physiologist. Families will be provided with standard information about follow up care with their primary care provider and contact information for Children's Hospital Colorado Diabetes and Child Health Clinics if needed regarding any abnormal study findings. In addition, the subject/family will be provided with copies of their study lab results, DEXA scan and physical activity monitoring. Study staff will also call the family within 6 months of after completion of the study to check-in on the recommended follow up care and answer any questions about test results. A results letter will be provided to the family about clinically relevant results obtained during the study. Participants will be encouraged to contact study staff with questions regarding the results letter.

Follow-up from Sleep study results:

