- 3) All subjects will complete a 3 day food questionnaire. This will be reviewed with them, and healthier food choices and meal planning will be discussed with both the subject and their parent by the PI or PRA, all of who are trained in providing diet prescriptions. Additionally, obese subjects will be counseled on a weight loss diet. Over 80% of obese adolescents are obese as adults, if they do not change their eating habits and lose weight when they are still a teen.

4) The participants will benefit from getting a sleep study during their overnight stay at the hospital and discovering if they have obstructive sleep apnea. Depending on the results they may be referred to sleep clinic for further evaluation of sleep apnea.

Evidence of Direct Benefit

We believe that this protocol is in the 405 risk category for pediatric research. Subjects can benefit from the above study measurements. Further, at the conclusion of the study, all subjects in the protocol will also be given counseling on the benefits of exercise as discussed above, and given an exercise prescription. The subjects may also be re-contacted once by phone call to follow-up on their study results and exercise recommendations. They may also be followed up in a clinical setting if PI notes further benefit of clinical follow up. Sedentary subjects will thus gain direct benefit from the study through the benefits of specialized counseling and recommendations for increased physical activity that would not otherwise be available to them.

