1. Serious Adverse Event Definition

Events are divided into those that are not serious (AE) and those that are serious (SAE). The distinction between an SAE and an AE is a regulatory definition established by the FDA, not a clinical definition. The definition of SAE is not always related to clinical severity of the event. For the purposes of this study an AE is considered a Serious (SAE) when it satisfies any one of the following criteria:

- The event results in an inpatient hospitalization (any overnight stay associated with an admission).
- The event results in the prolongation of a hospital stay.
- The event results in permanent or severe disability.
- The event results in death.
- The event is life-threatening.
- Treatment is required to prevent a serious event.

There have been no SAE's in the research groups experience in the Pediatric CTRC. We do not anticipate encountering SAE's; however, we have identified the following as possible SAE's for the purposes of monitoring:

- Infection related to blood draw or IV placement

a) Serious Adverse Event Reporting

Study patients are instructed to contact the clinic with any serious adverse event meeting the above criteria. Each SAE is recorded on the study form and the PI is informed as soon as possible after they occur and preferably within 24 hours of the notification of the clinic staff. This notification should occur even if data are incomplete. Additional data and follow-up information are documented and sent subsequently as an update to the original report. The PI immediately forwards SAE reports to the COMIRB and any other required institutional monitoring committee.

C. Subject Discontinuation Criteria

If a subject experiences any of the following, the subject will be withdrawn from the study.

1. Inability to complete study procedures
2. Abnormal screening labs (LFT's >150 IU, HbA1C>6.4%, Hg <10 mg/dL)
3. Subject becomes pregnant during study

D. Protocol Stopping Criteria

If one or more subjects experience any of the SAE's listed above, the PI will consult with the study staff prior to continuing study visits with subjects. The PI and RSA will consult about the significance of the SAE's and make a recommendation about subject continuation in the study.

VII. Data Analysis Plan:

Overall Project Statistical Plan:

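### After Visit 3, the only visit with an IV line and a draw of up to 300 ml, the adverse-event rule has no next visit to act at and no timed enquiry takes its place

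*Combined protocol and SAP*

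**What the plan says.** **When AEs are recorded.** Section VI.A, Adverse Event Reporting, says: "AEs are reported on a standard form that is completed by the study staff at each regular follow-up visit and phone interview". It continues: "Adverse events reported or ascertained between clinic visits are captured and reported at the time of the next scheduled visit".

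**What is scheduled.** Section III.C says: "The study consists of 3 visits - 2 outpatient visits and one overnight inpatient visit". The study calendar ends at Visit 3, and the compensation paragraph also treats the third visit as the last.

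**What happens at Visit 3.** Section III.D.2 (IV Risks) places one peripheral IV line, during the glucose tolerance test, and says: "Rarely, there is a risk of a blood clot forming or infection". Section III.D.1 (Blood Sampling) allows up to 300 ml at that visit.

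**What follows Visit 3.** The Lifestyle Prescription section says: "Study staff will also call the family within 6 months of after completion of the study to check-in on the recommended follow up care". It adds that the call is also for questions about test results. Section III.E, Evidence of Direct Benefit, says: "The subjects may also be re-contacted once by phone call to follow-up on their study results and exercise recommendations".

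**Serious events.** Section VI.B names one possible serious adverse event (SAE) for monitoring: "Infection related to blood draw or IV placement". Participants are told to contact the clinic about events that meet the SAE criteria, and the PI is then to be informed, preferably within 24 hours of the clinic staff being notified. Section VI.D says: "If one or more subjects experience any of the SAE's listed above, the PI will consult with the study staff prior to continuing study visits".

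**The concern.** The AE rule depends on a later visit at which staff can ask. That works for events after Visits 1 and 2. It does not work after Visit 3, where the exposure is greatest and where an infection or clot at the IV site could appear only after discharge. The call that might fill the gap has no target time. Its stated purpose is follow-up care, results and exercise advice, and two sections disagree on whether it must happen.

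What is at stake is whether the investigators learn, in reasonable time, of harm from the study's most invasive procedure in girls and young women aged 12 to 21. If nobody asks, a local infection treated by a family doctor may never be recorded. The record would then look clean partly because no question was put.

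**Working it through.** The protocol states no figure on this point to reproduce. The check sets its rules against its schedule.

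1. **Visits left after the IV line.** Visits planned (III.C): 3. The IV line is placed at Visit 3 (III.D.2). Scheduled visits afterwards: 3 − 3 = 0. Section III.D.7 says the MRI is usually done on the day of admission, so Visit 2 gives no routine later contact.

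2. **Exposure at that visit.** Blood at Visit 3 is up to 300 ml, against 11.5 ml at screening, or 25.5 ml for PCOS participants (III.D.1). Ratios: 300 / 11.5 = 26.1 and 300 / 25.5 = 11.8. An event from the screening draw can still be asked about at Visits 2 and 3, so the gap is specific to Visit 3.

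3. **Longest wait for an enquiry.** This depends on how two passages are read:

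| Reading of the later call | Latest AE enquiry after Visit 3 |
|---|---|
| It is the phone interview meant in VI.A, and it is mandatory (Lifestyle Prescription) | 6 months |
| It is optional (III.E), or it is not an AE enquiry | No limit |

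The 6 months takes study completion to mean the participant's own last visit. On neither reading is the call tied to a short period after Visit 3.

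4. **Which events have a route after Visit 3.**

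| Event | Route in the protocol | Does staff enquiry occur at a set time? |
|---|---|---|
| Serious, recognised and reported by the family | Participant contacts the clinic; PI informed; report forwarded (VI.B) | Not needed |
| Serious, not recognised or not reported | None until someone asks | No |
| Non-serious | Next scheduled visit (none exists) or phone interview (undefined) | No |

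The 24-hour target in VI.B runs from the moment clinic staff are notified, so it cannot help with an event nobody reports.

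5. **Number affected.** The enrolment table in III.C plans 80 overnight stays (4 groups × 20).

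6. **Chance that the gap matters.** The protocol gives no rate for IV-site infection or clot. As an assumption only, let p be the rate per participant of an IV-site event that appears after discharge. The chance of at least one among 80 is 1 − (1 − p)^80:

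| Assumed p | Chance of at least one |
|---|---|
| 0.1% | 0.08 |
| 0.5% | 0.33 |
| 1% | 0.55 |
| 2% | 0.80 |

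The range is wide and shows only that the answer depends on a rate the protocol does not supply.

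**The case against.** The strongest reply is that serious events, which are what the consultation rule in VI.D acts on, do not pass through the AE sentence at all. VI.B gives them a separate route, not tied to visits, and section VI requires the PI to report adverse events to the CTRC and COMIRB immediately. One of the SAE criteria, treatment needed to avert a serious event, could cover a treated infection. This stands. A reader might infer that the next-visit sentence delays the VI.D rule; the documents do not support that. Nor is the named infection clearly the only trigger, because the reference back in VI.D may cover all the SAE criteria.

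A reader might also infer that nobody speaks to families for six months. That goes too far. Sleep studies are read within 5 business days, 30–40% of participants are expected to need some follow-up, the PI notifies families of abnormal results, and a results letter invites questions. About half the participants have a patient relationship with the PI. These contacts are real, but most depend on a result or on the family, and none is described as an AE enquiry.

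The later call may well be the phone interview that VI.A has in mind, since it is the only call planned for all families. Even so, it could come at 6 months.

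The AE definition, limited to examination findings and laboratory results, might suggest that an event reported by phone cannot count. VI.A goes on to say that affirmative answers to questions are pursued, so participant reports do enter the assessment. What is missing is a plain statement that they count, and a time when the questions are put.

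It is tempting to project how many girls would pass through Visit 3 during the wait from the statement that over 100 were enrolled in 60 months. That figure is past enrolment across studies, not this study's Visit 3 rate, and cannot carry the projection. Section VI.B also reports no SAEs in the group's prior experience at the unit.

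**Conclusion.** The point holds as a gap in active enquiry after Visit 3. The AE rule in VI.A has no next visit to refer to, and no enquiry is timed to cover the IV line and the large draw. It applies to all 80 planned Visit 3 participants. The wait for any planned enquiry is up to 6 months if the later call is mandatory and counts as the phone interview, and open-ended otherwise. It mainly concerns non-serious IV-site or blood-draw events, together with serious ones that families do not recognise or report.

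The conclusion rests on the text of the schedule and the AE rules; it needs no assumed event rate. It does not touch the primary analysis, and the protocol plans no safety outcome or safety analysis that it would bias. It should be corrected as a matter of participant safety and consistent drafting.

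**What to change.** Reconcile the Lifestyle Prescription section, Evidence of Direct Benefit, VI.A and VI.B as follows:

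- Make a phone contact after Visit 3 mandatory, in a short window that the investigators set to cover the time in which an IV-site infection or clot would be expected to appear. Complete the standard AE form at that contact.
- Keep the later check on follow-up care, as a second brief call if needed, and complete the AE form then too. Moving the single call early would defeat its purpose of seeing whether recommended care took place.
- Word the call the same way in both sections, as certain rather than optional.
- State in VI.A that events reported by the participant or family count as AEs.
- Set an end date for AE collection that still captures abnormal laboratory results arriving after the first call, since VI.A counts these as AEs.

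The cost is a wording amendment and one extra brief call per participant, 80 × 1 = 80 calls as planned, with the staff time to complete the form. The protocol shows no budget for calls, so this should be treated as a small new cost. No extra visit or procedure is needed.
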